Plasma will also be serially obtained, for measurement of plasma cell-free tumor DNA (cfDNA) at baseline, Cycle 1 Day15, Cycle 3 D1 and at disease progression). This would allow us to determine biomarkers of response and/or resistance associated with FGFR inhibition.

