4.3 Intervention

Fulvestrant will be administered according to its approved dose of 500 mg intramuscularly on days 1, 15, 28 and then every 28 days (+/-3 days) thereafter. Debio 1347 will be administered orally daily (1 cycle is 28 days) and the dose of Debio 1347 could be de-escalated as detailed in section 4.1. The dosage in the phase 2 portion will be the MTD/RP2D determined in the phase 1b portion.

Pharmacokinetic and pharmacodynamic data will be obtained throughout the phase Ib/Phase II portion of the study. A baseline biopsy of a metastatic site will be required, with the acquisition of at least 3 fragments on a core biopsy for all the patients enrolled on the trial and in addition archival tissue will also be obtained, whenever available. Tissue will be evaluated for FGFR amplifications by FISH and protein and mRNA expression in collaboration with [name].

[figure not shown]
Plasma will also be serially obtained, for measurement of plasma cell-free tumor DNA (cfDNA) at baseline, at Cycle 1 Day 15, Cycle 3 Day 1 and at disease progression. This would allow us to determine biomarkers of response and/or resistance associated with FGFR inhibition.

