9.4 Dose Modifications or Scheduling Delays

- This study will use the NCI Common Toxicity Criteria (CTC) AE version 4.0 for toxicity.
- Study treatment will be temporarily or permanently discontinued due to the occurrence of AEs as specified in Table 1 below, for both the phase 1 and 2 portions of this study.
- Additionally, non-treatment related or unexpected toxicities may require interruption of therapy at the discretion of the Investigator.

- Failure to recover to the specified levels following temporary discontinuation within 7 days in the phase 1b portion and 14 days in the phase 2 portion will result in permanent treatment discontinuation. The treating Investigator and the PI will discuss the case of any patient whose treatment has been delayed for more than 7 or 14 days, respectively, who they think may benefit from continued treatment, prior to resuming treatment.
- In addition, if Grade 2 or higher toxicity occurs, treatment may be temporarily discontinued at the discretion of the Investigator. The patients may resume at the same dose level when toxicity has resolved to Grade 1 or below or the baseline level if resolution is achieved within 7 days in the phase 1b part and 14 days in the phase 2 part.
- In the event the patient requires temporary treatment discontinuation, the Investigator may choose to increase the frequency of the assessments performed to weekly collections until resolution.
- Only in the phase 2 portion, one dose reduction can be undertaken except for dose level -1 (60mg). Patients resuming treatment following a temporary discontinuation can do so at their original dose level or at one lower dose level.
- Patients experiencing a DLT during the DLT period may continue treatment after dose adjustments if there is a potential benefit from treatment after discussion with the PI
- Patients will be permanently discontinued if reduction beyond <60mg/day is necessary in both phase 1 and phase 2 portions of the study
- Reduced doses may not be re-escalated.
- If a patient discontinues Debio 1347 purely due to toxicity, they can stay on study and continue to receive fulvestrant. The patient will be captured as coming off of Debio 1347 due to toxicity and report TTF.

Table 1: Dose Modifications and Delays during Phase 1 and Phase 2

Adverse Event	Grade	Action	
		Phase I part: DLT evaluation period only	Phase I part: non-DLT evaluation period Phase 2 portion

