10.1 EVALUATION DURING TREATMENT/INTERVENTION

	Screening	Treatment							EOT	F/U ^a
Cycle		1				2		3+		Every 12 weeks
Day	-28 to -1	1	4	8	15	28	1	15	1	
		±2	±1	±2	±2	-4	±3	±3	±3	±7
										±14
Written Informed Consent	X									
Review of Eligibility Criteria	X									
Demographic Information	X									
Vital Signs, ECOG PS ^b	X	X			X		X	X	X	X
Height	X									
Physical Exam and Weight	X	X			X		X	X	X	X
12-lead ECG ^c	X	X				X			X	X
ECHO ^c	X								X	X
Haematology and Chemistry blood work ^d	X	X		X	X		X	X	X	X
Tumor markers (CEA and CA15-3)	X	X					X		X	X
Other Bloodwork (CRP LDH, uric acid and γGTP)	X	X		X	X		X	X	X	X
Phosphate (P)			X							
Blood coagulation (PT (INR), APTT)	X	X					X		X	X
Urinalysis ^e	X	X		X	X		X	X	X	X
Calcium regulating hormones bloodwork ^f	X	X					X		X	X
Serum pregnancy test	X									X
Ophthalmological testing ^g	X									X
Adverse events		X		X	X	X	X	X	X	

Fulvestrant		X			X	X			X		
Tumour assessment^h	X								X	X	
Plasma sample for CfDNAⁱ		X			X				X	X	
Pharmacokinetics^j		X			X		X		X		
Tumor Biopsy^k	X										
HepBsAg, HepBcAb, HIV and hepatitis C antibody^l	X										

Abbreviations: DEXA, dual-energy X-ray absorptiometry; ECHO, echocardiogram; ECOG, Eastern Cooperative Oncology Group; EOS, end-of-study; EOT, end-of-treatment (any study treatment); IV, intravenous; PS, performance status.

- a) Survival and disease status will be assessed every 12 weeks (+/- 14 days) until death, withdrawal of consent, or end of the study, whichever is first. Assessments can be collected through phone call or review of patient records.
- b) Blood pressure and heart rate to be collected. BP and pulse rate to be taken after at least 5 minutes of supine rest.
- c) ECG recorded every 3RD cycle *after* Cycle 3. If an ECG shows QTc prolongation (> 470 msec.), the ECG must be repeated twice additionally to obtain values in triplicate. ECHO will be done at baseline, every 3 cycles and at EOT during the phase 1 portion of the study.
- d) Haematology: red blood cells, haemoglobin, hematocrit, platelet count, white blood cells, neutrophils, lymphocytes, monocytes, eosinophils, basophils.
- Blood chemistry(Fasting): total protein, albumin, total bilirubin, AST, ALT, LDH, ALP, γ GTP, CK, total cholesterol, sodium (Na), potassium (K), calcium (Ca), chloride (Cl), phosphate (P), magnesium (Mg), creatinine, BUN, CRP, uric acid, glucose.
- e) Urinalysis: protein, blood, glucose, urobilinogen, pH, sediment, creatinine, calcium (Ca), phosphate (P).

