- f) Calcium regulating hormone assessments (whole-PTH, 1,25(OH) 2D, PTHrP) will be performed every cycle until Cycle 3 and every 3 cycles thereafter.
- g) Ophthalmological tests to be repeated as clinically indicated during treatment. Complete ophthalmologic examinations will be performed at screening and, as soon as clinically indicated, if a patient reports any visual abnormality. Complete ophthalmologic examination will be performed and interpreted by a qualified ophthalmologist, including visual acuity testing, slit-lamp ophthalmoscopy and indirect ophthalmoscopy. At the final visit and 28 days after the last dose, slit-lamp ophthalmoscopy will be performed.
- h) Tumor assessments (patients with a history of brain mets will be required to have brain CT scans with contrast or MRIs) to be performed every 8 weeks for 48 weeks (i.e. cycle 2, 4, 6 between days 22 and 28) and then every 12 weeks thereafter (i.e. cycle 9, 12, 15 again between days 22 and 28 etc.).
- i) Plasma samples for cfDNA analysis will be collected prior to dosing on cycle 1, cycle 1 day 15, day 1 of C3 and then at EOT.
- j) Plasma samples for PK will be collected both during phase 1 and 2. Phase 1 PK will be collected prior to dosing on day 1 and 15 of cycle 1 and then day 1 of each cycle thereafter. Phase 2 PK will be collected prior to dosing on day 15 of cycle 1 and day 1 of cycle 2.

k) Baseline tumor biopsies will be obtained during screening for all patients enrolled in the study, at least three fragments on a core biopsy

l) Documented negative tests prior to screening period is acceptable.

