10.1 Follow up visits

The mandatory End of Treatment Visit should be conducted approximately 2-4 weeks after the last dose of trial treatment or before the initiation of a new anti-cancer treatment, whichever comes first. All AEs that occur prior to the End of Treatment Visit should be recorded. Subjects with an AE of Grade > 1 will be followed until the resolution of the AE to Grade 0-1 or until the beginning of a new anti-neoplastic therapy, whichever occurs first. SAEs that occur within 30 days of the end of treatment or before initiation of a new anti-cancer treatment should also be followed and recorded.

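### The last cfDNA sample is set at disease progression in Sections 1.0 and 4.3 but at end of treatment in the schedule, so some progressions would have no scheduled sample

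*Combined protocol and SAP*

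**What the plan says.** **At progression.** Section 1.0 sets the cfDNA draws "at baseline, Cycle 1 Day15, Cycle 3 D1 and at disease progression". Section 4.3 repeats this: "at baseline, at Cycle 1 Day 15, Cycle 3 Day 1 and at disease progression". The stated purpose is to "determine biomarkers of response and/or resistance associated with FGFR inhibition". Section 2.1 lists this work as exploratory in both phases.

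**At EOT.** The cfDNA row of the schedule (Section 10.1, Evaluation during Treatment/Intervention) is marked at Cycle 1 Days 1 and 15, in the Cycle 3+ column and at EOT. The follow-up column is empty. Footnote i agrees with the row: "day 1 of C3 and then at EOT".

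**What EOT means.** The abbreviation list under the schedule gives "EOT, end-of-treatment (any study treatment". Section 10.1, Follow up visits, says: "The mandatory End of Treatment Visit should be conducted approximately 2-4 weeks after the last dose of trial treatment". The same sentence brings the visit forward if another anti-cancer therapy is about to begin. Under Section 10.1.3, Debio 1347 ends for progression, but also for toxicity, pregnancy, withdrawn consent or the investigator's judgment of the patient's interests. Section 9.4 adds: "If a patient discontinues Debio 1347 purely due to toxicity, they can stay on study and continue to receive fulvestrant".

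**After EOT.** Section 13.1 follows patients who stop without progression until they progress, for up to two years. Schedule footnote a lets follow-up information be gathered by telephone or from the chart.

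**Analysis.** Section 14.0 treats resistance biomarkers descriptively and graphically, with Fisher's exact or Wilcoxon tests if there are enough clinical benefit events. It has no rule for classifying a last sample from a patient who has not progressed.

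**The concern.** Two narrative sections and the operational schedule name different triggers for the same tube. Sites work from the schedule, so the EOT trigger is the one likely to be carried out.

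The question is whether the two triggers yield the same samples. If they do not, the set of last samples would mix patients whose disease had progressed with patients whose disease was still controlled, and some patients who do progress would have nothing drawn at that point. A missed draw cannot be recovered at analysis. What is at stake is the ability to compare baseline plasma with plasma at progression for the resistance objective.

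**Working it through.** The plan states no figure on this point, so there is none to reproduce. The check sets the sections side by side, then gives an illustrative range.

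**Step 1. Follow each route a patient can take.**

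| Route | Sections 1.0 and 4.3 | Schedule row and footnote i |
|---|---|---|
| Treatment stopped because of progression | Draw at progression | Draw at EOT, about 2-4 weeks after the last dose or sooner if new therapy starts; often close to progression |
| Progression, but treatment continues (brain-metastasis exception in 10.1.3; note in 13.1) | Draw at progression | Draw only when treatment finally ends, after progression |
| All treatment stopped without progression; progression found in follow-up | Draw at progression | Draw at EOT, before progression; none scheduled at progression |
| Debio 1347 stopped for toxicity, fulvestrant continued, then progression (9.4) | Draw at progression | Depends on which stop counts as EOT |

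The triggers roughly agree in the first row only.

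**Step 2. The fulvestrant-alone route.** The abbreviation list ties EOT to any study treatment, while the follow-up section times the visit from the last dose of trial treatment.
- If stopping Debio 1347 triggers EOT, the sample is taken before progression and none is scheduled when the patient later progresses.
- If EOT waits for the last fulvestrant dose, the sample may fall near progression, but after an unspecified time without the FGFR inhibitor.

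The documents do not say which applies.

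**Step 3. Is there other material at progression?** Tumor biopsy is marked at screening only (schedule row and footnote k), and archival tissue predates treatment. The last plasma draw is therefore the only tumor-derived material that the plan could supply at progression.

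**Step 4. Size.** The input from the documents is the phase 2 maximum of 43 (Section 14.0). Section 9.2.1 says that all phase 1 patients were already off study, so phase 2 is what an amendment can still affect. The share stopping without progression is not given; 5% to 30% is an assumption. Affected last samples = share x N.

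- 0.05 x 43 = 2.15, about 2
- 0.10 x 43 = 4.3, about 4
- 0.20 x 43 = 8.6, about 9
- 0.30 x 43 = 12.9, about 13

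If the trial stops after stage 1 with 18 patients, the range is 0.05 x 18 = 0.9 to 0.30 x 18 = 5.4, or about 1 to 5.

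**The case against.** The strongest reply is that this is an editorial mismatch in an exploratory component. For most patients who stop because of progression, EOT will be near progression. The data needed to sort the samples are already collected: Section 10.1.4 records the reasons for discontinuation together with the EOT results of withdrawn patients, and Section 9.4 captures toxicity stops. Sections 1.0 and 4.3 still call for a progression draw, so a careful site might take one anyway.

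Much of that stands, and it rules out several stronger readings that a reader might infer:

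- **That EOT samples will be analysed as resistance samples, or pooled with progression samples.** No section says so. What is missing is a rule, and the recorded reasons for stopping would allow one.
- **That every EOT sample is taken 2-4 weeks off drug.** The interval is approximate and is cut short when new therapy starts.
- **That washout makes the sample unrepresentative.** At the 14-hour half-life in Section 3.3.4, 14 x 24 / 14 = 24 and 28 x 24 / 14 = 48 half-lives. That describes plasma Debio 1347. The documents say nothing about how long acquired alterations stay detectable in cfDNA.
- **That the first-in-human results give the rate of non-progression stops.** The 49% is for dose modification and the 32% for related events of grade 3 or higher, across 10 to 150 mg. Neither is a discontinuation rate.

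The reply does not close the sampling gap. Recorded reasons can classify a tube that was drawn, but cannot supply one that was never scheduled.

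**Conclusion.** The contradiction is real, and it changes which samples exist. Under the schedule, some last samples will come from patients without progression, some will come after progression, and a patient who progresses after a non-progression stop has no scheduled draw. Whether stopping Debio 1347 alone counts as EOT is undefined.

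Under the assumed 5% to 30%, about 2 to 13 of at most 43 phase 2 samples would not be linked to progression when drawn. How many of those patients later progress without a sample cannot be derived from the documents.

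The consequence is limited to the exploratory resistance objective. The clinical benefit endpoint, the two-stage decision rule and its error rates do not depend on it. The change is still worth making because the loss is irreversible and most of the remedy is moving a tube already planned.

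**What to change.** 1. Amend the cfDNA row and footnote i to match Sections 1.0 and 4.3: after the Cycle 3 Day 1 sample, draw at the visit where progression is first documented. Naming the first documentation matters because Section 12.2 asks for confirmation at least 4 weeks later, which would otherwise leave two candidate visits.
2. Let the EOT sample stand in only when progression is the reason for EOT and no progression-visit sample exists.
3. State whether stopping Debio 1347 while fulvestrant continues triggers EOT for sampling purposes. For these patients, schedule a draw at progression on study.
4. In Section 14.0, restrict the resistance comparison to samples linked to documented progression, using the discontinuation reasons already recorded, and describe other EOT samples separately.

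The cost is a wording amendment and an occasional extra tube for a patient who progresses after an earlier EOT draw. Patients followed only by telephone or chart may still lack a progression sample unless they attend in person, so the report should state how many progressions have none. Treatment and its stopping rules are not affected.

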10.1 Follow up visits

The mandatory End of Treatment Visit should be conducted approximately 2-4 weeks after the last dose of trial treatment or before the initiation of a new anti-cancer treatment, whichever comes first. All AEs that occur prior to the End of Treatment Visit should be recorded. Subjects with an AE of Grade > 1 will be followed until the resolution of the AE to Grade 0-1 or until the beginning of a new anti-neoplastic therapy, whichever occurs first. SAEs that occur within 30 days of the end of treatment or before initiation of a new anti-cancer treatment should also be followed and recorded.

10.1.2 Survival Follow-up

Once a subject experiences confirmed disease progression or starts a new anti-cancer therapy, the subject moves into the survival follow-up phase and should be contacted by telephone or review of patient records every 12 weeks to assess for survival status until death, withdrawal of consent, or the end of the study, whichever occurs first.

10.1.3 End-of-Treatment Criteria

Treatment with Debio 1347 will continue until any of the following occur:

- Patient withdraws consent.
- Disease progression documented by CT scan, physical exam or other objective method of measurement. An exception could be made for patients who progressed due to brain metastases; patients may continue treatment with Debio 1347 if, in the Investigator's opinion, there was reasonable evidence of ongoing clinical benefit.
- Unacceptable toxicity.
- Pregnancy.
- Patient's interests as judged by the Investigator.
- In the event of a Debiopharm International SA decision to no longer supply study drug, ample notification will be provided so that appropriate adjustments to subject treatment can be made.

Patients who are removed from study treatment due to AEs are to be treated and followed-up according to accepted medical practice. All pertinent information concerning the outcome of such treatment will be recorded.

10.1.4 End-of-Treatment Visit

Patients will undergo the EOT assessment and exit from the study, unless they are prematurely discontinued from the study for any of the following reasons:

1. Patient requests to leave the study.
2. Adverse event, e.g. intercurrent illness that would, in the judgment of the Investigator, affect assessments of clinical status to a significant degree; or intercurrent illness that, in the opinion of the Investigator compromises the patients safety.
3. Patient non-compliance.
4. Patient lost to follow-up.
5. If, in the Investigators opinion, continuation in the trial would be detrimental to the patient's wellbeing.
6. A major protocol violation occurs.
7. Prohibited medication as indicated in Section 9 is required/used during the course of the trial. In the event a patient is found to be taking a prohibited medication during the trial, the site should immediately contact the Medical Monitor. The decision to withdraw the patient will be made in conjunction with the Sponsor.
8. Non-drug related reason; e.g. patient relocates too far from study centre.
9. Study is terminated.

Should a patient be withdrawn, EOT assessments should be performed prior to any further therapeutic intervention whenever possible. Results of these assessments will be recorded together with a description of the reasons for study discontinuation.

10.1.5 Correlative analyses

Plasma samples for pharmacokinetics (PK) will be collected during both phase 1 and 2. Phase 1 PK will be collected prior to dosing on day 1 and 15 of cycle 1 and then day 1 of each cycle thereafter. Phase 2 PK will be collected prior to dosing on day 15 of cycle 1 and day 1 of cycle 2. These samples may be analyzed by LC-MS/MS to assess the PK (trough levels at steady-state) of both fulvestrant and Debio 1347 in combination. These data will be compared with historical PK data in monotherapy (Faslodex® prescribing information; PK results from Study Debio 1347-101), in order to investigate potential PK interactions and to support interpretation of safety and/or efficacy results in the trial, and tumor specimens will be studied.

Archival tissue will be obtained, whenever available as well.

Baseline tumor biopsies will be obtained. We will perform FISH, protein and mRNA expression analyses from formalin-fixed paraffin-embedded tissue samples in the laboratory of [name] along with the MSKCC Integrated Genomics Operation (IGO) and MSKCC Molecular Cytogenetics Core facilities.

- 1) ***FGFR1* FISH** will be performed as follows: *FGFR1* amplification will be assessed using the Zytolight SPEC FGFR1/CEN 8 Dual Color Probe (Zytovision, Bremerhaven, Germany). Tissue processing, hybridization, post-hybridization washing, and fluorescence detection will be performed according to standard lab procedures. Slides will be scanned using a Zeiss AxioPlan 2i epifluorescence microscope equipped with a CCD camera (CV-M4+CL, JAI) controlled by Isis 5.5.9 (MetaSystems Group Inc.). Marked region(s) within a given tissue section will be scanned at 63X or 100X and at least five images per representative region captured, each image being a compressed stack of 12 z-section images taken at 0.5 μ m intervals. Signal counts will be performed on the captured images and a minimum of 100 discrete nuclei scored. Amplification will be defined as >10 copies of discrete *MYB* or *NF1B* signals or small cluster of signals (>4 copies; representing tandem duplications/repeats). Tumors will be considered as *FGFR1*-amplified under one of the following conditions: a) The *FGFR1*/CEN8 ratio is ≥ 2.0 ; b) Average number of *FGFR1* signals per tumor cell nucleus is ≥ 6 ; or c) Presence of large or small cluster of signals *FGFR1*/CEN8 ratio will be also reported as a continuous variable.
- 2) **Immunohistochemistry:** the expression of *FGFR1* at the protein level will be assessed using immunohistochemistry, using the monoclonal D8E4 antibody (Cell Signaling, Boston, MA). Antibody dilution and antigen retrieval is currently being optimized. Stained slides will be analyzed in a semi quantitative manner using the H score method.
- 3) **mRNA expression:** We will quantify the mRNA expression levels of *FGFR1* along with other key targets using Nanostring. RNA will be extracted the RNAeasy Mini Kit (Qiagen) according to the manufacturers' instructions. One hundred ng of total RNA will be hybridized to a custom designed gene CodeSet (non-enzymatic RNA profiling using barcoded fluorescent probes) according to the manufacturers protocol (Nanostring Technologies). Barcodes will be counted (600 fields of view per sample) on an nCounter Digital Analyzer following the manufacturer's instructions (NanoString® Technologies) and normalized to housekeeping transcripts. Further analysis will follow previously published methods to identify the range of *FGFR1* expression levels, which will be compared to IHC and FISH findings.

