4.1 OVERVIEW OF STUDY DESIGN/INTERVENTION

4.2 Design

This is an open-label, single institution, phase Ib/phase II non-randomized trial that evaluates the safety, tolerability and anti-tumor activity of fulvestrant and Debio 1347 in patients with ER+/HER2- metastatic breast cancer (MBC) that are FGFR-amplified (as confirmed by a CLIA certified laboratory).

The phase I portion of this trial will have 2 dose levels: dose level 1 (80mg) and a de-escalation level (60mg) if the 80mg dose level has intolerable toxicities (N= minimum 4 and maximum 12). Fulvestrant will be administered intramuscularly at standard doses (500 mg loading dose on days 1, 14, and 28 of the first month, then maintenance dosing every 28 days, ± 3 days) with no dose-escalation. Only the dose of Debio 1347 will be de-escalated as shown below. There will be no intra-patient dose escalation. 1 cycle = 28 days.

The Dose Limiting Toxicity (DLT) observation period includes Day 1 to Day 28 of Cycle 1, plus the assessments prior to drug administration on Cycle 2, Day1.

Cohort/Dose level	Debio 1347	Fulvestrant
-1	60mg	500mg IM
1 (Starting dose cohort)	80mg	500mg IM

If none *or* one of the initial 3 patients in dose level 1 has DLT, 3 additional patients will be treated at the same dose level. If 2 or more patients experience DLT at this dose level, then dose level -1 will be evaluated. Should 2 or more patients experience DLT at dose level -1, the study will stop accrual. If only 1 of the 3 initial patients experiences a DLT at dose level -1, 3

additional patients will be evaluated at this dose level. Patients who withdraw before completing a full cycle of treatment for reasons other than development of a DLT will be replaced.

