5.2 Fulvestrant

Fulvestrant 500 mg should be administered intramuscularly into the buttocks slowly (1 - 2 minutes per injection) as two 5 mL injections, one in each buttock, on days 1, 15, 28 and once every 28 days as per standard of care.

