9.1 TREATMENT/INTERVENTION PLAN

This is an open-label, single institution, phase Ib/phase II non-randomized trial that evaluates the safety, tolerability and anti-tumor activity of fulvestrant and Debio 1347 in patients with ER+/HER2- metastatic breast cancer (MBC) that are FGFR-amplified (as confirmed by a CLIA certified laboratory).

The phase I portion of this trial will evaluate 2 dose cohorts (dose level 1 (starting dose level) 80mg Debio 1347, and dose level -1, 60mg Debio 1347). Fulvestrant will be administered at standard doses. Only the dose of Debio 1347 will be de-escalated as per section 4.1.

Phase 2 portion: The phase 2 portion will be comprised of an optimal Simon two-stage design to determine the efficacy of Debio 1347 plus fulvestrant (N: 18 in the first stage with possibility of going on to 43 if 3 out of the first 18 have a CBR \geq 24 weeks). The dosage in the phase 2 portion will be the MTD/RP2D determined in the phase 1b portion (**80mg daily**), except that concomitant prophylaxis for hyperphosphatemia will not be required.

1 cycle: 28 days. Patients will be on treatment until progression of disease or unacceptable toxicity.

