The hepatic oxidative metabolism of Debio 1347 has been shown in vitro to be mainly mediated by CYP 4F3b, with no or only minor contribution of other metabolic enzymes. Furthermore, according to bi-directional permeability experiments in Caco-2 cells, Debio 1347 is not a substrate of P-glycoprotein (P-gp) or breast cancer resistance protein (BCRP) efflux transporters. Therefore, based on current knowledge, Debio 1347 appears to have a low risk of being victim of PK interaction from other drugs. In contrast, as per in vitro results available so far and Debio 1347 plasma exposure achieved in patients, Debio 1347 is considered at possible risk of perpetrating drug-drug interactions through CYP3A inhibition, CYP3A induction (some transporters such as P-gp might also be co-induced), CYP1A2 repression, or inhibition of several transporters (P-gp, BCRP, multidrug and toxin extrusion protein 1 [MATE1], organic cation transporter 2 [OCT2]; bile salt export pump [BSEP] is also inhibited).

The clinical impact of these in vitro observations is not known. While patients are not precluded from receiving any drugs based upon the potential for a PK drug interaction, patients who are taking concurrent drugs that are known substrates of either CYP3A, CYP1A2, P-gp, BCRP, MATE1 or OCT2 should be carefully monitored.

Notably, due to the irreversible nature of CYP3A inhibition by Debio 1347 and also its in vitro potential for enzyme induction, it should be noticed that the potential for drug-drug

interactions with CYP3A substrates (and possibly also with P-gp substrates) is time-dependent; it may increase with time as patients continue to take Debio 1347, and it may persist for some days after Debio 1347 discontinuation.

A list of drugs that are sensitive or narrow-therapeutic-range substrates of CYP3A, CYP1A2, and substrates of P-gp, BCRP, MATE1 or OCT2 can be consulted in:

- Flockhart DA. Drug Interactions: Cytochrome P450 Drug Interaction Table. Indiana University School of Medicine (2007): <http://medicine.iupui.edu/clinpharm/ddis/table.aspx>, and
- <http://www.fda.gov/Drugs/DevelopmentApprovalProcess/DevelopmentResources/DrugInteractionsLabeling/ucm093664.htm>

If treatment with a prohibited medication is necessary, the patient will be withdrawn from the study.

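### Neither scheduled Phase 2 PK sample is a steady-state fulvestrant trough, so setting Phase 2 fulvestrant levels against historical troughs would mix time since injection with any Debio 1347 effect

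*Combined protocol and SAP*

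**What the plan says.** Section 10.1.5 (Correlative analyses) states that the samples may be analysed "to assess the PK (trough levels at steady-state) of both fulvestrant and Debio 1347 in combination". Fulvestrant results are to be set against its prescribing information and Debio 1347 results against the sponsor's earlier study, to look for PK interactions and help interpret safety and efficacy.

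Sampling times, from footnote j of the schedule table (section 10.1) and section 10.1.5:
- Phase 2: "Phase 2 PK will be collected prior to dosing on day 15 of cycle 1 and day 1 of cycle 2".
- Phase 1: before dosing on Days 1 and 15 of Cycle 1, then on Day 1 of every later cycle.

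Fulvestrant injection days:
- Section 4.3: "500 mg intramuscularly on days 1, 15, 28 and then every 28 days (+/-3 days) thereafter".
- Section 5.2: "on days 1, 15, 28 and once every 28 days as per standard of care".
- Section 4.2: "500 mg loading dose on days 1, 14, and 28 of the first month".
- Schedule table: marked at Cycle 1 Days 1, 15 and 28 and at Day 1 of Cycle 3 onward; not marked at Cycle 2 Day 1. The PK row is marked at Cycle 2 Day 1 but not at Cycle 1 Day 28.

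**The concern.** A trough is the level at the end of a dosing interval, just before the next dose. On the written schedule the Cycle 2 Day 1 visit has no fulvestrant dose for the sample to precede; the only dose due that day is the daily Debio 1347. The fulvestrant level drawn there belongs to the start of a 28-day interval, not its end.

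If such a level is compared with a published trough, the two differ in time since injection as well as in the presence of Debio 1347, and the comparison cannot separate these. Phase 2 is the larger cohort (up to 43 patients, two samples each), and section 14.0 analyses exploratory endpoints separately by phase, so Phase 1 data would not fill the gap.

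**Working it through.** The plan gives no sample size, expected level or margin for the PK comparison, so there is no figure of its own to reproduce. The check is day arithmetic, followed by a sensitivity calculation on assumed values.

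**1. Study days.** Section 9.1: "1 cycle: 28 days. Patients will be on treatment until progression of disease or unacceptable toxicity". With Cycle 1 Day 1 as day 1, Cycle 2 Day 1 = 28 + 1 = day 29 and Cycle 3 Day 1 = 56 + 1 = day 57.

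**2. Cycle 2 Day 1 sample.** Nominal gap from the Day 28 injection: 29 − 28 = 1 day. The table allows Day 28 to be up to 4 days early (days 24 to 28) and Cycle 2 Day 1 to move by 3 days (days 26 to 32).
- Shortest gap: 26 − 28 = −2 days (sample before injection).
- Longest gap: 32 − 24 = 8 days.

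If the 3-day fulvestrant window of section 4.3 is applied to Day 28 instead (days 25 to 31), the gap runs from 26 − 31 = −5 to 32 − 25 = 7 days. Either way, time since injection varies between patients by 10 to 12 days.

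**3. Cycle 1 Day 15 sample.** With the second injection on Day 15, the sample is taken before it, 15 − 1 = 14 days after one injection: a pre-injection level, but not steady state. With the Day 14 of section 4.2, it would fall 15 − 14 = 1 day after the second injection. Neither case gives a steady-state trough.

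**4. Phase 1 from Cycle 3.** The table puts fulvestrant on Cycle 3 Day 1, so a pre-dose sample there is 57 − 28 = 29 days after the Day 28 injection and precedes the next one. Counting 28 days from Day 28, as section 4.3 does, gives day 56, one day before that visit; the 3-day window covers the difference, but the order of injection and sample then needs recording.

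**5. Debio 1347.** Section 3.3.4 gives a 14-hour half-life. By Cycle 1 Day 15, 14 × 24 = 336 hours have passed, or 336/14 = 24 half-lives; the fraction of steady state is 1 − 2^(−24), above 99.99%. Taking the stated 1.7-fold accumulation instead, 1/(1 − e^(−24k)) = 1.7 gives a half-life of 18.7 hours and still above 99.99%. Both Phase 2 samples are valid steady-state troughs of Debio 1347.

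**6. Possible size for fulvestrant (assumption only).** The documents give no fulvestrant half-life or absorption rate. I assumed elimination half-lives of 20 to 50 days and absorption half-lives of 0.01 to 4 days. One injection contributes ka/(ka − ke) × (e^(−ke·t) − e^(−ka·t)), with each rate equal to ln 2 divided by its half-life. Contributions were added for injections on days 1, 15 and 28. The reference is the steady-state trough under 28-day dosing.

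| Assumed elimination half-life | Day 29 level, with vs without Day 28 injection | Day 29 level vs steady-state trough | Day 15 level vs steady-state trough |
|---|---|---|---|
| 20 days | 1.14 to 1.97 | 1.70 to 3.21 | 0.88 to 1.01 |
| 30 days | 1.12 to 1.78 | 1.18 to 2.02 | 0.58 to 0.66 |
| 40 days | 1.11 to 1.70 | 0.91 to 1.49 | 0.44 to 0.49 |
| 50 days | 1.10 to 1.66 | 0.74 to 1.18 | 0.35 to 0.39 |

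Ranges within a row come from the absorption half-life. The Day 29 level can lie above or below the steady-state trough.

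**The case against.** Several points on the other side stand.

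- A reader might infer that the whole historical comparison is invalid. It is not. There are two comparisons, one per drug, and the Debio 1347 one is sound. Debio 1347 is also the drug named in the exploratory PK objective (section 2.1).
- The plan as a whole does contain pre-injection fulvestrant samples, in Phase 1 from Cycle 3 on, though from at most 12 patients.
- The one-day gap is nominal. The windows allow some samples before the injection. The first-line fulvestrant trial cited in section 3.1.1 counts from Day 0, which would put the third injection on day 29; a sample before it would be a loading-phase trough, still not a maintenance one. What the documents prove is that injection days and sampling days have not been reconciled.
- Section 10.1.5 speaks of historical PK data, not of troughs in so many words. That the comparator is a trough follows from calling the samples steady-state troughs. A comparison matched on time since injection is not ruled out, but nothing requires it.
- Section 9.1.2 says of the interaction with CYP3A substrates that "it may increase with time as patients continue to take Debio 1347". A reader might infer that early sampling will miss a growing effect on fulvestrant. The documents never say that fulvestrant is a CYP3A or P-gp substrate, so that does not follow.
- The analysis is optional and exploratory, and no decision rule uses it.

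These points narrow the finding. None makes either Phase 2 sample a steady-state fulvestrant trough.

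**Conclusion.** The concern holds for fulvestrant in Phase 2. Of the two scheduled samples per patient, none is by design a steady-state trough, so the description in section 10.1.5 is wrong for that drug. This conclusion needs only the stated days and the schedule table read by column.

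A comparison of those levels with historical troughs would be confounded by time since injection. It would be tempting to add that the result would look like a raised fulvestrant level caused by Debio 1347. The documents do not support this: on assumed half-lives the ratio to the steady-state trough runs from 0.7 to 3.2, so even the direction is open.

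The consequence is limited to an exploratory, optional analysis. The clinical benefit endpoint and the two-stage design are not affected.

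**What to change.** 1. Reconcile the fulvestrant injection days in sections 4.2, 4.3 and 5.2 and the schedule table with each other and with the PK sampling days. Which injection schedule applies is for the investigator and sponsor to confirm.
2. Record the actual date and time of each injection and each PK sample.
3. In section 10.1.5, use the Cycle 2 Day 1 samples of both phases as troughs for Debio 1347 only. For fulvestrant, either leave them out of the trough comparison or compare them with historical levels at the same time since injection. Describe Cycle 1 Day 15 as an early, not a steady-state, fulvestrant sample. For Phase 1 this is a change of analysis only, since section 9.2.1 says its patients were already off study.
4. Optionally, draw the second Phase 2 fulvestrant sample before the injection at Cycle 3 Day 1, a visit that already carries fulvestrant and cfDNA.

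Items 1 to 3 cost a few sentences and two recorded times, with no extra blood draws. Item 4 has a real cost: patients who stop at the first scan (Cycle 2, days 22 to 28) would lack that sample. If it replaced Cycle 2 Day 1 altogether, they would have only one PK sample for either drug. Nor can the documents show that fulvestrant is at steady state 29 days after the third injection. Item 4 is therefore an option, not a requirement.
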